2.6 Analysis of the key secondary objective

The key secondary objective in this study is to estimate efficacy of PDR001 using the duration of response per RECIST 1.1 and based on tumor response data per BIRC.

2.6.1 Key secondary endpoint

Duration of response (DOR) only applies to patients whose best overall response is complete response (CR) or partial response (PR) according to RECIST 1.1 based on BIRC review of tumor assessment data. The start date is the date of first documented response of CR or PR (i.e., the start date of response, not the date when response was confirmed), and the end date is defined as the date of the first documented progression or death due to underlying cancer.

2.6.2 Statistical hypothesis, model, and method of analysis

DOR will be listed and summarized for all patients in the FAS with confirmed BOR of CR or PR. The duration of response will be presented graphically along with the duration of on-study follow-up and information about responses. The distribution of duration of response will be estimated using the Kaplan-Meier method and the median duration of response will be presented along with 95% confidence interval only if a sufficient number of responses is observed. A responders-only analysis will also be performed in this case.

2.6.3 Handling of missing values/censoring/discontinuations

For DOR analysis patients continuing without progression or death due to underlying cancer will be censored at the date of their last adequate tumor assessment using the censoring rule described for PFS analysis.

2.7 Analysis of secondary efficacy objective(s)

All secondary efficacy endpoints according to RECIST 1.1 or irRECIST will be based on tumor assessments as per BIRC. The local radiology assessments will be used as supportive analysis.

Antitumor activity (assessed by ORR and DoR per RECIST 1.1 and BIRC) in each of the three well-differentiated NET cohorts (pancreatic, GI, thoracic) will also be evaluated as secondary endpoint.

2.7.1 Secondary endpoints

Disease control rate (DCR)

DCR is defined as the proportion of patients with best overall response of CR, PR or SD according to RECIST 1.1 criteria and as per central review. DCR will be calculated using FAS and based on the BIRC tumor assessments.

Time to response

Time to response (CR or PR) is the time from date of treatment start to first documented response of CR or PR (which must be confirmed subsequently) using BIRC review of tumor assessment data and according to RECIST 1.1. All patients in the FAS will be included in the time to response calculation. Patients who did not achieve a confirmed PR or CR will be censored at:

- the maximum follow-up time (i.e. FPFV - LPLV used for the analysis) for patients who had a PFS event (i.e. either progressed or died due to any cause);
- the last adequate tumor assessment date for all other patients.

Progression-free survival (PFS)

PFS is defined as the time from the date of first dose to the date of the first documented radiological progression or death due to any cause. PFS will be assessed via central review according to RECIST 1.1. PFS will be censored if no PFS event is observed before the analysis cut-off date.

If a patient has not progressed or died at the analysis cut-off date, PFS will be censored at the date of the last adequate tumor evaluation date before the cut-off date. PFS events documented after the initiation of new anti-neoplastic therapy (i.e. RECIST 1.1. documented disease progression or death) will be considered provided tumor assessments continue after initiation of new cancer therapy. Discontinuation due to disease progression (collected on the 'End of treatment' and 'End of post treatment follow up' disposition pages) without supporting objective evidence satisfying progression criteria per RECIST 1.1 will not be considered disease progression for PFS derivation.

Efficacy endpoints according to irRECIST

Immune related overall response rate (irORR) is the proportion of patients with a best overall response of irCR or irPR based on BIRC review of tumor assessment data.

The best immune related overall response for each patient is determined from the sequence of immune related overall responses according to rules described in the irRECIST appendix of the protocol.

Immune related duration of overall response (irDOR): For patients with a confirmed irCR or irPR based on BIRC review of tumor assessment data. The start date is the date of first documented confirmed response and the end date and censoring is defined the same as that for time to progression.

Date of confirmed response is derived as followed: Response (irPR or irCR) should be confirmed by a second assessment no less than 4 weeks after the first assessment showing response. Date of response is then the date of the first of these two assessments. For confirmation of irCR the two assessments must be consecutive (intervening assessments of irUNK are permissible). For confirmation of irPR the two assessments do not need to be consecutive, but must not be separated by a pseudo-progression event.

Immune related time to overall response (irTTR) is the time between date of start of treatment until first documented response (confirmed irCR or irPR).

Immune related disease control rate (irDCR) is the proportion of patients with a best overall response of irCR or irPR or irSD. Patients with BOR of irNCRNPD will also be included in DCR if patients with non-measurable disease at baseline are in analysis set.

Immune related progression-free survival (irPFS) is the time from date of start of treatment to the date of event defined as the first documented assessment of irPD that was then confirmed or death due to any cause. Unconfirmed irPD without further adequate tumor assessments will be considered as a confirmed irPD. If a patient has not had an event, progression-free survival is censored at the date of last adequate tumor assessment. An adequate tumor assessment is a tumor assessment with overall response other than irUNK.

Immune related confirmed irPD is derived as described in section 5.5.

Overall survival rate at 1 year and 2 years

OS is defined as the time from date of start of treatment to date of death due to any cause. If a patient is not known to have died, then OS will be censored at the latest date the patient was known to be alive (on or before the cut-off date).

2.7.2 Statistical hypothesis, model, and method of analysis

Disease control rate

DCR will be calculated based on the FAS. DCR and its 95% confidence interval will be presented.

Time to response

TTR will be listed and summarized for all patients. The distribution of time to response will be estimated using the Kaplan-Meier method only if a sufficient number of responses is observed.

Progression-free survival (PFS)

PFS based on RECIST 1.1 will be analyzed in the FAS population. The PFS distribution will be estimated using the Kaplan-Meier method, and the Kaplan-Meier curves, medians and 95% confidence intervals of the medians will be presented for all patients.

Number of patients with a PFS event and number of patients censored for the PFS analysis will be summarized. In addition, a summary of reasons for PFS censoring will be provided based on the following reasons:

- 1: Ongoing without event

- 2: Lost to follow-up
- 3: Withdrew consent
- 4: Adequate assessment no longer available
- 5: Event after ≥ 2 missing tumor assessments

The PFS censoring reasons are defined in the following way.

If the time interval between the last adequate tumor assessment (TA) date and the earliest of the following dates is smaller or equal to interval of 2 missing TAs:

1. Analysis cut-off date,
2. Date of consent withdrawal,
3. Visit date of study treatment discontinuation or end of post-treatment follow-up discontinuation due to lost to follow-up.

Then the PFS censoring reason will be:

1. 'Ongoing',
2. 'Withdrew consent',
3. 'Lost to follow-up',

If the time interval is larger than the interval of 2 missing TAs with no event observed. then the PFS censoring reason will always default to 'Adequate assessment no longer available'. If the time interval between the last adequate TA date and the PFS event date is larger than the interval of 2 missing TA then the patient will be censored and the censoring reason will be 'Event documented after two or more missing tumor assessments'. Further details on the definition of last adequate assessment and two missing TAs are provided in [Section 2.7.3](#).

Efficacy endpoints according to irRECIST

The following irRECIST endpoints will be analyzed in a similar way to the corresponding RECIST endpoints:

- irORR
- irDoR
- irTTR
- irDCR
- irPFS.

Overall Survival

The survival distribution of OS distribution will be estimated using the Kaplan-Meier method and Kaplan-Meier curves.

Survival estimates at 1 year and at 2 years will be computed with 95% confidence interval [[Brookmeyer and Crowley 1982](#)].

2.7.3 Handling of missing values/censoring/discontinuations

If a patient is not known to have died at the time of analysis cut-off, then OS will be censored at the date of last known date patient was alive, i.e., last contact date.

The date of last adequate tumor assessment is the date of the last tumor assessment with overall lesion response of CR, PR or SD or non-CR/non-PD before an event or a censoring reason occurred. In this case the last tumor evaluation date at that assessment will be used. If no post-baseline assessments are available (before an event or a censoring reason occurred) then the start date of treatment will be used.

In particular, PFS will be censored at the last adequate tumor assessment if one of the following occurs: absence of event; the event occurred after two or more missing tumor assessments. The term “missing adequate tumor assessment” is defined as a tumor assessment not performed or tumor assessment with overall lesion response of “UNK”. The rule to determine number of missing TAs is based on the time interval between the date of last adequate tumor assessment and the date of an event. If the interval is greater than twice the protocol-specified interval between the TAs and 2 times the protocol-allowed time window around assessments, then the number of missing assessments will be 2 or more.

As per protocol, tumor assessments are expected to be performed every 8 weeks for the first 12 months and every 12 weeks thereafter.

Therefore:

- if the last adequate tumor assessment is performed before end of week 36 (i.e. from study day 1 to study day $36*7=252$) then the interval of 2 missing tumor assessments is given as $2*8+2=18$ weeks (126 days);
- if the last adequate tumor assessment is performed from end of week 36 up to end of week 44 (i.e. from study day 253 to study day $44*7=308$) then the interval of 2 missing tumor assessments is given as $8+12+2=22$ weeks (154 days);
- otherwise, when the last adequate tumor assessment is performed after end of week 44 (i.e. from study day $44*7+1=309$ onward), then the interval of 2 missing tumor assessments is given as $2*12+2=26$ weeks (182 days).

These summaries on censoring reasons will be produced for PFS by investigator and BIRC.

Refer to [Table 2-5](#) for censoring and event date options and outcomes for PFS.

Table 2-4 Outcome and event/censor date for PFS analysis

Situation	Date	Outcome
No baseline assessment	Date of start of treatment	Censored
Progression or death at or before next scheduled Assessment	Date of progression (or death)	Progressed
Progression or death after exactly one missing assessment	Date of progression (or death)	Progressed

Situation	Date	Outcome
Progression or death after two or more missing assessments	Date of last adequate assessment prior to missed assessment	Censored
No progression (or death)	Date of last adequate assessment	Censored
Treatment discontinuation due to 'Disease progression' without documented progression, i.e. clinical progression based on investigator claim	Date of last adequate assessment	Censored
New anticancer therapy given prior to protocol defined progression	Ignore the new anticancer therapy and follow situations above	As per above situations
Death before first PD assessment	Date of death	Progressed

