3.2.10 Sensitivity analyses

This section outlines the possible event and censoring dates for progression, as well as addresses the issues of missing tumor assessments during the study. For instance, if one or more assessment visits are missed prior to the progression event, to what date should the progression event be assigned? And should progression event be ignored if it occurred after a long period of a patient being lost to follow-up? It is important that the protocol and RAP specify the primary analysis in detail with respect to the definition of event and censoring dates and also include a description of one or more sensitivity analyses to be performed.

Based on definitions outlined in [Section 3.2.7](#), and using the draft FDA guideline on endpoints (Clinical Trial Endpoints for the Approval of Cancer Drugs and Biologics, April 2005) as a reference, the following analyses can be considered:

Table 3-2 Options for event dates used in PFS, TTP, duration of response

Situation		Options for end-date (progression or censoring) ¹ (1) = default unless specified differently in the protocol or RAP	Outcome
A	No baseline assessment	(1) Date of randomization/start of treatment ³	Censored
B	Progression at or before next scheduled assessment	(1) Date of progression (2) Date of next scheduled assessment ²	Progressed Progressed
C1	Progression or death after exactly one missing assessment	(1) Date of progression (or death) (2) Date of next scheduled assessment ²	Progressed Progressed
C2	Progression or death after two or more missing assessments	(1) Date of last adequate assessment ² (2) Date of next scheduled assessment ² (3) Date of progression (or death)	Censored Progressed Progressed
D	No progression	(1) Date of last adequate assessment	Censored
E	Treatment discontinuation due to 'Disease progression' without documented progression, i.e. clinical progression based on investigator claim	(1) Ignore clinical progression and follow situations above (2) Date of discontinuation (visit date at which clinical progression was determined)	As per above situations Progressed
F	New anticancer therapy given	(1) Ignore the new anticancer therapy and follow situations above (ITT approach) (2) Date of last adequate assessment prior to new anticancer therapy (3) Date of secondary anti-cancer therapy (4) Date of secondary anti-cancer therapy	As per above situations Censored Censored Event

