Situation		Options for end-date (progression or censoring) ¹ (1) = default unless specified differently in the protocol or RAP	Outcome
G	Deaths due to reason other than deterioration of 'Study indication'	(1) Date of last adequate assessment	Censored (only TTP and duration of response)
^{1.} =Definitions can be found in Section 3.2.7 . ^{2.} =After the last adequate tumor assessment. "Date of next scheduled assessment" is defined in Section 3.2.7 . ^{3.} =The rare exception to this is if the patient dies no later than the time of the second scheduled assessment as defined in the protocol in which case this is a PFS event at the date of death.			

The primary analysis and the sensitivity analyses must be specified in the protocol. Clearly define if and why options (1) are not used for situations C, E and (if applicable) F.

Situations C (C1 and C2): Progression or death after one or more missing assessments: The primary analysis is usually using options (1) for situations C1 and C2, i.e.

- (C1) taking the actual progression or death date, in the case of only one missing assessment.
- (C2) censoring at the date of the last adequate assessment, in the case of two or more consecutive missing assessments.

[figure not shown]
In the case of two or missing assessments (situation C2), option (3) may be considered jointly with option (1) in situation C1 as sensitivity analysis. A variant of this sensitivity analysis consists of backdating the date of event to the next scheduled assessment as proposed with option (2) in situations C1 and C2.

Situation E: Treatment discontinuation due to 'Disease progression' without documented progression: By default, option (1) is used for situation E as patients without documented PD should be followed for progression after discontinuation of treatment. However, option (2) may be used as sensitivity analysis. If progression is claimed based on clinical deterioration instead of tumor assessment by e.g. CT-scan, option (2) may be used for indications with high early progression rate or difficulties to assess the tumor due to clinical deterioration.

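### SAP Table 2-4 censors a patient who stops for undocumented clinical progression even if that patient dies within the assessment window, a death the rest of the SAP counts as a PFS event

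*SAP*

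**What the plan says.** SAP 2.7.1 defines PFS as time to "the first documented radiological progression or death due to any cause". It censors only when no such event is seen by the cut-off. It also says that a stop for progression without objective RECIST evidence is not progression, but does not make that stop a reason to censor.

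The text of SAP 2.7.3 names two grounds for censoring: no event, or an event after two or more missing assessments. The second is decided by the gap from the last adequate assessment: more than 126, 154 or 182 days, depending on when that assessment took place. Without any post-baseline assessment, the gap runs from treatment start. SAP 2.7.2 lists five censoring reasons, and clinical progression is not one of them.

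The table that follows is captioned Table 2-4, although the text calls it Table 2-5. Five of its rows matter here:

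- Stop for progression "without documented progression, i.e. clinical progression based on investigator claim": date of last adequate assessment, censored.
- "Progression or death at or before next scheduled Assessment": date of progression or death, event.
- "Progression or death after two or more missing assessments": date of last adequate assessment, censored.
- New anticancer therapy: "Ignore the new anticancer therapy and follow situations above".
- "Death before first PD assessment": date of death, event, with no time limit.

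In Protocol Appendix 1, Table 3-2, the default for situation E (clinical progression claimed by the investigator) is "1) Ignore clinical progression and follow situations above". Section 3.2.10 adds: "Clearly define if and why options (1) are not used for situations C, E and (if applicable) F". SAP Section 4 declares one change from the protocol, the dropped evaluation of heterogeneity between cohorts, and no other.

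**The concern.** A patient who stops for clinical deterioration and dies soon afterwards, before another scan, fits two rows of Table 2-4 with opposite outcomes. The table gives no order of precedence. Two programmers could both follow the SAP and classify the same death differently.

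The literal reading of the clinical-progression row is the harmful one. The patients it censors are those who were getting worse, so the censoring is informative and makes the Kaplan-Meier PFS curve look better than it is. At stake are the PFS estimates, which are secondary and descriptive.

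The death row raises a second, smaller ambiguity. Read alone, it makes a death an event however late it occurs, whereas the two-missed-assessments rule censors late deaths.

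**Working it through.** **1. The SAP's windows.** Scans are every 8 weeks and later every 12 weeks, each with a window of one week either side. SAP 2.7.3 adds two scan intervals and two window weeks:

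- (8 + 8 + 2) × 7 = 126 days
- (8 + 12 + 2) × 7 = 154 days
- (12 + 12 + 2) × 7 = 182 days

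All three match the SAP.

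**2. Clinical stop, then death inside the window.** Last adequate scan Day 113 (week 16: 16 × 7 + 1), clinical stop Day 130, death Day 150. The next scan is due on Day 169 (24 × 7 + 1). The gap is 150 − 113 = 37 days, within 126.

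- SAP 2.7.1, the SAP 2.7.3 text, the row for an event by the next scheduled assessment, and the Appendix 1 default: event at Day 150.
- Clinical-progression row: censored at Day 113. None of the five reasons in SAP 2.7.2 describes this censoring.

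**3. Same stop, death outside the window.** Last adequate scan Day 57, death Day 184. The gap is 184 − 57 = 127 days, more than 126. The Appendix 1 default sends this patient to the two-missed-assessments rule, so both it and the clinical-progression row censor at Day 57. The first conflict is therefore limited to deaths inside the window.

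**4. Neither documented progression nor death.** Both rules censor at the last adequate assessment, so there is no difference.

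**5. Possible size of the first conflict.** The documents do not say how many patients stop this way, so every input below is an assumption. In the simulation (200,000 patients per scenario):

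- time to progression is exponential with median 2, 4 or 8 months, with the protocol scan schedule and 13 months of follow-up;
- 5% to 30% stop for clinical progression;
- 80% or 50% of these are rescanned, with progression documented 14 days later, and count as events under both rules;
- the rest die unscanned, after a mean of 1 or 3 months.

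Rise in 6-month PFS (Day 183) when the row is applied instead of the Appendix 1 default:

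- 80% rescanned: 0.001 to 0.017
- 50% rescanned: 0.003 to 0.044
- Middle case (median 4 months, 10% stop, 80% rescanned, death after a mean of 1 month): 0.385 to 0.390, or about 0.005, with about 1.6 deaths per 95 patients turned into censored times

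For scale, the binomial standard error at 0.385 with 95 patients is √(0.385 × 0.615 / 95) ≈ 0.05, about ten times the middle-case shift.

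**6. The death row.** For a patient with no post-baseline scan, the gap is counted from Day 1.

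- Death Day 127: 127 − 1 = 126, an event under both rules.
- Death Day 128: 128 − 1 = 127 > 126, an event at Day 128 under the death row but censored at Day 1 under the two-missed-assessments rule.

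Let S be the 6-month PFS of the other patients, assumed exponential with median 4 months: S = exp(−ln 2 × 182 / (4 × 30.4375)) = 0.355. Counting one such death as an event instead of censoring it at Day 1:

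- death Day 128 to 183 lowers 6-month PFS by S/n: 0.355/95 = 0.004, or 0.355/21 = 0.017;
- later death raises it by (1 − S)/n: 0.645/95 = 0.007, or 0.645/21 = 0.031.

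The direction depends on when the death falls.

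**The case against.** The best defence is that the rest of SAP 2.7 settles the reading. Death from any cause is an event, only two grounds for censoring are named, and no censoring reason exists for clinical progression. On that view the row only says that a clinical claim is not itself an event. This is a sensible intention, but the table does not state it. The row would then duplicate the row for patients without progression or death, and its label excludes documented progression, not death. The next row shows that the authors had the right wording available.

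Four stronger readings might be inferred, and the documents do not support them:

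- **The Appendix 1 default rescues every later death.** It does not. It passes the patient to the other situations, which censor deaths beyond the window.
- **A later documented progression is dropped as well.** The row is limited to patients without documented progression, and the PFS definition counts such progression.
- **The SAP may not depart from the default.** Appendix 1 lets the analysis plan specify otherwise (Table 3-2 header, Section 4.1). What is missing is the stated reason and a declaration in SAP Section 4.
- **Duration of response is biased too.** SAP 2.6.3 applies the PFS censoring rule to responders continuing without progression or cancer death, and SAP 2.6.1 makes cancer death the end date. No effect on DOR has been shown.

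The defence is also right that the number affected is likely to be small. Before the primary cut-off, the protocol requires prompt imaging on clinical suspicion (7.2.3), an end-of-treatment scan if none was done within 30 days (Table 7-2), and scanning after treatment stops (7.1.8). Appendix 1, Section 4.4 asks for review of undocumented stops. The simulation does not model the end-of-treatment scan, which would reduce the effect further.

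**Conclusion.** The clinical-progression row is wrong as written. For a death within 126, 154 or 182 days of the last adequate assessment, it contradicts the PFS definition, the SAP's own grounds and reasons for censoring, and the protocol default. Applied literally, it removes true events and biases descriptive PFS upward.

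The size rests on assumed stop and rescan rates and is probably small: about 0.005 at 6 months in the middle case, and up to 0.044 only if 30% stop clinically and half of them are never rescanned. The ORR success rule is not affected.

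The death-row ambiguity is a secondary wording point. It is real for a never-scanned patient who dies on Day 128 or later. The documents give no count of such patients, and the effect on PFS can go either way.

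**What to change.** Replace the entry in the clinical-progression row with the Appendix 1 default, to ignore the clinical claim and follow the situations above, and set the outcome to match, as the new-therapy row does. If the sponsor does intend to censor these deaths, give the reason that Appendix 1, Section 3.2.10 requires and list the change in SAP Section 4.

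Add one sentence on precedence between the death row and the two-missed-assessments rule. SAP 2.7.2 and 2.7.3 support applying the 18/22/26-week rule to deaths, counted from treatment start when there is no post-baseline scan. The opposite order is also workable, provided it is stated.

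The cost is one table row, one sentence and the matching programming before database lock, with no new data. Compared with the literal row, the first change can make PFS look slightly shorter; the second can move it in either direction.
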